9. SAFETY

As there is no study medication, there will be no adverse events to report. Risks linked to study procedures are low and described in paragraph 2.3.

Serious Adverse Events (SAE) reporting

Serious Adverse Events can relate to medicines or refer to other domains.

This study is an interventional study because we collect biosamples from the participants, but no treatment interventions are foreseen, and no systematic data collection on medicines will be performed. Therefore no Serious Adverse Events related to medicines can be defined.

Serious Adverse Events related to this interventional study (not medication-related) are defined as events which result in any of the following:

- Death
- Life-threatening experience
- Inpatient hospitalisation during participating in the study
- Persistent or significant disability/incapacity
- Congenital anomaly or birth defect

All Serious Adverse Events (SAE's) identified during the study will be reported to the Sponsors, while only fatal SAE's will be reported to the Sponsors and CNER by the Principal Investigator within seven days. A Follow-up Report will then be sent once the SAE is resolved.

Reports will identify subjects by unique code (Participant ID) rather than by the subjects' names or other Personally Identifiable Information.

Protection of the nurses in contact with the participants will be ensured by several measures :

- Biosafety procedures (dressing/undressing procedure, security equipment to be used, decontamination procedure) have been developed based on procedures from the Sanitary Inspection and validated by [name]. Nurses will also receive training by the Sanitary Inspection.
- Duration of inclusion visit will be shortened as much as possible, by making a maximum of steps by phone, in particular the explanation of the study and the data collection for the ISARIC CRF (see informed consent collection process)

No paper will be taken out of the home from the participants (see also informed consent collection process).

Reporting Pregnancy

Pregnancy is not an AE, but data on pregnancy before study entry or occurring during the study will be collected.

Procedure in case of SARS-CoV-2 detection RT-PCR result within study related sampling

RT-PCR will be performed at each follow-up visits and may allow detection of SARS-Cov-2 in particular during visits at 6, 15 and 24 months. Any positive result for RT-PCR has to be declared to the Sanitary Inspection. So if the RT-PCR test result is positive for SARS-CoV-2, a delegated clinical member of the study team will be informed and proceed to de-identify the participant. Then a delegated clinical team member will contact the participant to inform about the result, instruct him/her to contact the treating physician (or the governmental hotline in case there is no treating physician), and refer him/her for a diagnostic validation in an accredited laboratory. The prescription for the regular, care-based diagnostic test will be provided by a study physician delegated by the PI, or by the treating physician indicated in the (e)ICF. If the participant agrees, the sample taken for research purposes can be forwarded to an accredited laboratory. A referral letter with the laboratory study results will be provided to the treating physician if requested by the study participant.

10 DATA MANAGEMENT

Data will be collected through 3 different ways:

- 1/ Questionnaires using the ePRO module of Ennov Clinical: health status monitoring data with daily questionnaires during the 14 first days following diagnosis, then weekly questionnaires at weeks 3 and 4 and monthly questionnaires from month 2 to month 12. A unique link to the questionnaires will be sent by email to participants which will fill in the questionnaire online. Participants can choose to answer or not to the questionnaires. For children > 10 years, adapted questionnaires will be filled in directly by the child. For children < 10 years, no questionnaires will be sent.
- 2/ Adapted ISARIC CRF : at hospital and at inclusion for patients included from home. For patients at home data collection will be performed by phone by the CIEC team.
- 3/ CoLive LIH smartphone application (LIH in-house solution): innovative data (voice recordings and mini-questionnaires). For adults and children > 10 years.

Data in the ISARIC adapted CRF will be completed by a trained nurse or CRA from CIEC. Access to source data during hospitalisation will be provided by the different participating hospitals and/or by the e-santé national database. Data collection is the responsibility of the clinical trial staff at the site under the supervision of the site investigator. The investigator is responsible for ensuring the accuracy, completeness, legibility, and timeliness of the data reported.

In the e-questionnaires and the CoLive-LIH application, the patient will be responsible for the data entry.

Each data collection tool (e-questionnaires, ISARIC, CoLive LIH) implements its own data collection rules and controls, to ensure that data is entered correctly at the earlier stage of the data handling process. Each variable input will be controlled as soon as it is entered by the authorized user with allowable values, min and max values when necessary, consistency controls between relevant variables, allowable values filtering according to the context already fulfilled, etc.

Data handling will be carried out through specific edit checks to test the consistency of the database. Quality controls will also be regularly performed according to the clinical and epidemiological good practice guidelines.

A Clinical Data Management Plan will be provided to authorized people manipulating the data (which includes detailed description of source documentation, CRFs, instructions for completing forms, value coding dictionaries and reconciliation processes, data handling procedure and procedures for data monitoring). ISARIC adapted CRF and e-questionnaires are provided in annex of the present protocol.

Depending on the data collection path of the different tools provided to patients and the CIEC data collection team (nurses, CRA), each dataset will be centralized at LIH by the research team in order to link the patients' records and analyze them.

Since each collection tool uses its own pseudonym for the patients, LIH's research team manages a unique and secure pseudonymization matrix, enabling them to link all the patients' records coming from different sources.

As each eCRF and collection application manages its own coding standards, pooling of datasets needs to be curated and automated:

- generate an extra pseudonym for each patient in the pseudonyms matrix table, one unique for all datasets to enable the linkage;
- transform each dataset toward a unique coding standard / dictionary (NB: a unique codebook describing the target dataset will be written: each variable name, coding standard, allowable values, limit values, constraints);
- load the result in a central and secured database;
- execute global quality controls to avoid duplicates, check consistency and exhaustiveness.

This process is quite important and will be automated to avoid any quality discrepancy as far as data collection is on different platforms and at different timelines.

Therefore, the research team will be able to analyze collected and centralized data with all the relevant tools: SAS, SPSS, R or machine learning tools. Some extracts may be performed to allow researchers to load sub-datasets into their own analysis environments, but the central database will be secured and organized to avoid updates or deletion operations.

Following the good practices, when data is provided to researchers for further research projects, LIH's Data Management team will generate an extra pseudonym - added to the pseudonyms matrix table - for the extracted patients' records. The central codebook will be shared with the new research team.

11 STATISTICAL CONSIDERATIONS AND PLANNED INTERIM ANALYSES

11.1 Statistical hypotheses

N.A.

11.2 Sample size determination

This is a very early study which aims at understanding the severity associated with a new, poorly understood pathogen. Therefore, the sample size is not formally determined as in a clinical trial study. Recruitment of participants will depend on the emergence and spread of the virus and the resources available to the recruitment centres. The sample size should be as large as feasible and preferably without limit in order to capture as much clinical data as possible early in the outbreak. This is as well feasible because of the implementation of a national digital solution for follow up of patients.

Nevertheless, in the sub-sample study a minimum of 200 COVID-19 positive adult persons in the Predi-COVID study would allow to find a risk ratio of severe disease above 2 for the selected risk factor with a power of 80% when the prevalence of the disease is above 7% (see figure below). This number will be updated depending on new acquired knowledge (amendment to the protocol).

In the pediatric sub-sample study a minimum of 100 COVID-19 positive children in the Predi-COVID study would allow to find a risk ratio of severe disease above 3.2 for the selected risk factor with a power of 80% when the prevalence of the disease is above 7% (see figure below). This number will be updated depending on new acquired knowledge (amendment to the protocol).

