| Number of patients/ participants | 
The objective is to recruit virtually all COVID-19 positive persons in Luxembourg.
 
A sub-sample of a minimum of 200 COVID-19 positive persons in Predi-COVID study would allow to find a risk ratio of severe disease above 2 for the selected risk factor with a power of 80% when the prevalence of the disease is above 7%.
 
A minimum of 100 COVID-19 positive children would allow to find a risk ratio of severe disease above 3.2 for the selected risk factor with a power of 80% when the prevalence of the disease is above 7%.
 |
| Safety | No AE/SAE reporting is planned in this study since no interventional medication involved. |
| Statistical methods and data analysis | 
Descriptive statistics will be produced for hospitalisation, intensive care / resuscitation admission, ventilation, their duration, death and severity of the disease. Other variables including potential prognostic factors of the disease will also be described with mean (+- STD) or frequencies (%) as adequate. Statistical models will be used to study whether the risks of hospitalisation, intensive care admission or intubation as well as death are associated with a specific risk factor. adjustment will be done on age, gender and other potential confounding factors.
 
Further stratification of the patient cohort will be performed through Machine learning techniques to include biological and other omics measurements. According to a deep phenotyping of the symptoms of the disease as well as biosampling allowing for laboratory-based and computational analytics, a stratification approach will include data-driven tools and allow to define disease trajectories that will be translated into clinical and/or biomarker-defined subgroups.
 |
| Interim Analyzes | Regular interim analyses will also be performed to inform policy stakeholders. It will be mainly descriptive statistics on the main endpoints defined above. |
| Regulatory | 
The study will be submitted for approval at MS* and CNER**.
 
The study will follow the new General Data Protection Regulation (GDPR) of 27 April 2016.
 
Written informed consent will be obtained before enrolment in the study.
 
*Ministry of Health, **National Research Ethics Committee
 |

| | |
|-------------------------------|--|

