5. STUDY DESIGN

[figure not shown]

Figure 1. Overview of Predi-COVID design and data collection.

Predi-COVID is a prospective cohort study composed of people positively tested for COVID-19 in Luxembourg, followed with a remote system for monitoring participants' health evolution and symptoms. After explicit consent, virtually all adults ≥ 18 years and all children < 18 years with confirmed COVID-19 infection (positive by RTqPCR test) could be included in the Predi-COVID cohort.

A sub-sample of a minimum 320 adults and 100 children will be included in the deep-phenotyping sub-study. This number will be adapted to quickly evolving knowledge on COVID-19 and to the resources available to include and sample patients.

For hospitalized patients, the protocol encompasses a face-to-face inclusion combined with daily evaluations up to death or discharge (using ISARIC modified CRF (CORE + DAILY modules)). From discharge, participants will then be asked to enter the "Home" protocol. At home, a digital follow-up thanks to a remote system (web or mobile app) and the CoLive LIH smartphone app will be performed for both health status and symptoms checks as well as for research-oriented data collection.

Adult and child participants in Predi-COVID will be actively followed for 14 days from the time of confirmation of diagnosis, whether they are at the hospital or at home in isolation or quarantine. Short evaluations will be also performed at week 3 and week 4 and then monthly for a period up to 12 months to assess potential long term consequences of COVID-19.

A biological sampling is performed at baseline and at 6 months for all Predi-COVID participants.

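### For a binary risk factor at 7% risk of severe disease, neither sub-sample gives the 80% power stated in 11.2, and the adult minimum is 200 in five places but 320 in section 5

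*Protocol*

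**What the plan says.** Section 11.2 first says that the sample size is not formally determined. It then makes two power statements for the sub-samples:

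- Adults: at least 200 positive adults "would allow to find a risk ratio of severe disease above 2 for the selected risk factor with a power of 80" per cent; the condition attached reads "with a power of 80% when the prevalence of the disease is above 7" per cent.
- Children: "a minimum of 100 COVID-19 positive children in the Predi-COVID study would allow to find a risk ratio of severe disease above 3.2", with the same power and the same 7% condition.

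Both refer to a figure. The synopsis repeats both claims, the first as "A sub-sample of a minimum of 200 COVID-19 positive persons in Predi-COVID study would allow to find a risk ratio of severe disease above 2".

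The synopsis, 2.2, 6, 6.4 and 11.2 put the adult (or unqualified) sub-sample at 200. Section 5 says: "A sub-sample of a minimum 320 adults and 100 children will be included in the deep-phenotyping sub-study".

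**The concern.** Inclusion requires a positive PCR, so the disease whose prevalence exceeds 7% cannot be COVID-19 itself. The workable reading is the risk of severe disease, either in the unexposed or overall. At 7%, 200 adults yield few severe cases (14 if the risk is overall), which is a thin basis for finding a doubling of risk with 80% power. The 100 children would yield 7.

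These are the only planning figures for the principal objective, factors associated with severity. A reader who trusts them would take a null result for a binary factor as evidence against a risk ratio of 2 in adults or 3.2 in children. The two adult minimums also leave it unclear which number the statement should rest on.

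**Working it through.** **Inputs from the protocol.** N = 200 adults with RR = 2; N = 100 children with RR = 3.2; power 80%; rate 7% (11.2 and synopsis). N = 320 adults (section 5).

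**Assumptions, because the text available does not give them.** Binary factor, two groups, alpha 5% (two-sided unless stated), no dropout, exposed share f varied from 2% to 95%.

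**Formula.** With n1 = fN exposed, n0 = N − n1, p1 = RR × p0 and p̄ the pooled risk:

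power = Φ[(p1 − p0 − z·se0)/se1], where se0 = √{p̄(1 − p̄)(1/n0 + 1/n1)} and se1 = √{p0(1 − p0)/n0 + p1(1 − p1)/n1}.

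**Attempt to reproduce 80%, half exposed, 7% in the unexposed.**

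- Adults, 100 vs 100, 0.07 vs 0.14: p̄ = 0.105, se0 = 0.0434, se1 = 0.0431. (0.07 − 1.96 × 0.0434)/0.0431 = −0.35, so power is 36%.
- Children, 50 vs 50, 0.07 vs 0.224: p̄ = 0.147, se0 = 0.0708, se1 = 0.0691. (0.154 − 1.96 × 0.0708)/0.0691 = 0.22, so power is 59%.

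Fisher's exact test gives 29% and 48%. The 80% is not reproduced.

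**Other exposed shares, and 7% as the overall risk** (then p0 = 0.07/(1 − f + f × RR)). Two-sided power in per cent:

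| Setting | 50% exposed | 20% | 10% | Best over f |
|---|---|---|---|---|
| Adults 200, 7% unexposed | 36 | 33 | 25* | 38 |
| Adults 200, 7% overall | 25 | 29 | 24 | 30 |
| Adults 320, 7% unexposed | 53 | 45 | 33 | 54 |
| Adults 320, 7% overall | 37 | 39 | 31 | 42 |
| Children 100, 7% unexposed | 59 | 53 | 42 | 60 |
| Children 100, 7% overall | 30 | 42 | 37 | 42 |

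*26 if rejections in the wrong direction are counted.

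A one-sided 5% test, with 7% in the unexposed, reaches at most 50% (200 adults), 66% (320 adults) and 71% (children).

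**What 80% would take, two-sided.**

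- Keeping N and RR, at 50:50: an unexposed risk of about 17% for 200 adults, 12% for 320 adults and 10% for 100 children.
- Keeping 7% unexposed risk and RR, at 50:50: about 300 per group (600 adults) and 82 per group (164 children).
- Keeping N and 7% unexposed risk, the detectable RR is:

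| Sub-sample | 50% exposed | 10% exposed |
|---|---|---|
| 200 adults | 2.9 | 4.2 |
| 320 adults | 2.5 | 3.4 |
| 100 children | 4.0 | 5.7 |

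**Other readings tried.**

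- 7% as the prevalence of the risk factor: 80% then needs an unexposed severe risk of about 37% (adults) and 22% (children). The text states neither.
- N taken per group, at 50:50: 63% and 87%.
- Continuous factor, odds ratio per SD. The simple logistic formula is Φ[√(N × 0.07 × 0.93) × ln OR − z]. Adults: 3.608 × 0.693 = 2.50, giving 71% two-sided and 80% one-sided. Children: 2.551 × 1.163 = 2.97, giving 84% and 91%. A calculation from the logistic information matrix with 7% overall risk gives 76% and 80% one-sided.

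**The case against.** The strongest reply is that 11.2 points to a figure, which is not available here. That figure may state alpha, sidedness, the scale of the factor and what the 7% means. Many sub-cohort measures in 4.2 are quantitative and the planned model is logistic. A one-sided test of an odds ratio per SD comes near the stated values, as shown above. This stands as a limit on the finding. A reader might infer that the 80% is false under any assumptions, or that the plan omits alpha and the exposed share; with the figure unseen, the documents support neither. But the text says risk ratio, and for a risk ratio on a binary factor the missing settings do not help: no exposed share, with either a one- or a two-sided 5% test, reaches 80%.

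A second reply is that 11.2 disclaims formal sizing, calls the numbers minimums open to amendment, and that 11.3 analyses all patients enrolled. It is true that no decision rule hangs on the 80% and that clinical factors can be studied in the whole cohort. Yet both the synopsis and 11.2 go on to make a quantitative claim about the sub-samples, and that claim can be checked.

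Third, 7% is only a lower threshold, and severe disease may be commoner. If so, power rises, but the threshold given for 80% is still too low.

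Two further inferences should be resisted. One is that an effect of the stated size would usually be missed in children. With 7% in the unexposed, power is 53% to 59% at 20% to 50% exposed, so it would be found slightly more often than not. The other is that 320 is simply the updated adult number. Section 5 does not say so, and 11.2 still rests its claim on 200.

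**Conclusion.** The concern holds in limited form. Read as a risk ratio for a binary factor compared in two groups (pooled normal approximation, two-sided 5%, no dropout), the stated 80% is not attained. The most that any exposed share gives is 38% for 200 adults and 60% for 100 children with 7% in the unexposed, or 30% and 42% with 7% overall. Using 320 adults does not rescue the claim.

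A null result for a binary factor could therefore not rule out a risk ratio of 2 in adults, where the effect is more likely to be missed than found. Nor could it rule out 3.2 in children, where it would be missed in about 40% of cases or more. The conclusion does not extend to a continuous factor with an odds ratio per SD, and the figure cited in 11.2 could show that something like this was meant.

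Separately, and without any calculation, section 5 contradicts five other places on the adult minimum.

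**What to change.** In 11.2 and the synopsis:

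1. State alpha, sidedness, whether the factor is binary or continuous, and the exposed share.
2. Replace the reference to prevalence of the disease by the risk of severe disease in the unexposed.
3. Restate what is detectable with 80% power at 7% unexposed risk and two-sided 5%, for 50% down to 10% exposed: risk ratios of about 2.9 to 4.2 with 200 adults (2.5 to 3.4 if 320 is the intended minimum) and about 4.0 to 5.7 with 100 children. If an odds ratio per SD was meant, say so and give that calculation.

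Then use one adult minimum in the synopsis and in sections 2.2, 5, 6, 6.4 and 11.2, and derive the figures from it.

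The cost is wording. No participants are added and the design does not change, but the stated sensitivity becomes less favourable.

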11.3 Populations for analyses

All patients enrolled.

11.4 Statistical analyses

Descriptive statistics will be produced for the main endpoints, namely hospitalisation, intensive care / resuscitation admission, ventilation, their duration, death and severity of the disease. Secondary endpoints together with other variables including potential prognostic factors of the disease will also be described with mean (+- STD) or frequencies (%) as adequate.

A logistic model will be used to study whether the risks of hospitalisation, intensive care admission or intubation as well as death are associated with a specific risk factor. adjustment will be done on age, gender and other potential confounding factors.

Factors triggering the severity of the disease will be evaluated with a Mantel-Haenszel chi square to evaluate if different levels of patients' characteristics are associated with a more serious form of the disease.

Further stratification of the patient cohort will be performed through Machine learning techniques to include biological and other omics measurements. A deep phenotyping related to the symptoms of the disease as well as biosampling allowing for laboratory-based and computational analytics will be performed. The stratification approach will include data-driven tools and allow to define disease trajectories that will be translated into clinical and/or biomarker-defined subgroups

The time to conversion from the PREDI-COVID-H cohort to the PRECOVID cohort will also be studied.

[figure not shown]
Missing data will not be replaced concerning the endpoints. A replacement method such as multiple imputations through chained equations will be envisaged for the other variables and risk factors.

The limits of the study linked to the size of the sample enrolled, the extent of the effects or the selection of participants and other potential limits will be evaluated and discussed.

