| 
Ancillary study
 | 
An ancillary study will be added (Predi-COVID-H). For patients included as well as subjects living with positively tested patients on the basis of a volunteer informed consent.
 
Predi-COVID-H is an ancillary cohort study composed of Household members of index cases to monitor symptoms and disease outbreak in this high-risk population. For every asymptomatic member of the family of a “case” included in the Predi-COVID sub-sample (a “contact”), clinical as well as socio-economic characteristics will be collected. Biological samples will also be collected at the same time as the “case” visit by nurses and up to 50 ml of blood, nasopharygeal and oropharyngeal swabs, stool, saliva and hair samples will be taken at baseline for adults and children. According to the new recommendations of the Health Directorate, all Household contacts of positive cases are invited by the Sanitary Inspection to be tested 5 days after the diagnostic test of the “index case”. In case of positive result, the “contact” will be proposed to be enrolled in the Predi-COVID study. Otherwise, a second visit will be planned 6 months later, to collect blood, nasopharygeal and oropharyngeal swabs, stool, saliva and hair samples. All “contacts” will be followed digitally.
 
Predi-COVID-H inclusion criteria:
 
 ● Adult and children (0-17 ans) house members of COVID-19 positive participants. 
Exclusions criteria :
 
 ● Patients not understanding French or German 
Sample size: A minimum of 100 participants (adults and children) will be included in the sub-study on house-members. The sample size and the sampling strategy may have to be adapted to the rapidly evolving knowledge on COVID-19.
 |
|-------------------------------|--|

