7.3 Ancillary study: Predi-COVID-H

The samples and data collected during the study course are described in the table below. The Predi-COVID-H participants will be able to participate either to data collection only or to both data and sample collection. For sample collection they can choose to do all or part of the sampling. Since the national recommendations for the follow-up of contact persons of positive cases have recently changed with the prescription of a PCR test 5 days after the test of the case person, we adapted our sampling strategy with a follow-up visit conditioned by the PCR test result.

| Predi-COVID-H | | | |
|--|---|--|--|
| | Inclusion | Follow-up | |
| | | If RTqPCR prescribed by Sanitary Inspection results = negative | If RTqPCR prescribed by Sanitary Inspection results = positive |
| Informed consent | X (e-consent for data collection and written consent for sample collection, but stored electronically) | | |
| Data collection : online questionnaires (for adult participants and children > 10 years) | | Data collection daily for up to 14 days | |
| CoLive LIH application (optional, for adults and children >10 years) | | Regular voice recordings + short questionnaires | |

| | | | |
|--|---|--------------|--|
| Blood sample : up to 50mL (for children, volume adapted to child's weight) | X | X (6 months) | |
| Nasopharyngeal swab | x | x (6 months) | |
| Oropharyngeal swab | x | x (6 months) | |
| Stools | x | x (6 months) | |
| Hair sample | x | x (6 months) | |
| Sputum/saliva | x | x (6 months) | |
| End of study | | | X (contacts with positive PCR will be proposed to be enrolled in the Predi-COVID cohort and to start the follow-up at inclusion visit Predi-COVID) |

➤ **Predi-COVID-H biological characterization (according to sample type) (not exhaustive)**

Blood sample :

- **Antibodies to SARS CoV2**
- Immunophenotyping
- TRC repertoire
- Antibodies to CoV OC43, NL63 and 229E (optional)

Stool :

- SARS-CoV-2 and other CoV specific RT-PCR
- Microbiome-omics

Sputum/saliva :

- cell number, eosinophilic cationic protein, IL8, fibrinogen (optional)

Hair :

- hormones/glucocorticoid concentration

Swabs :

- SARS-CoV-2 and other CoV specific RT-PCR
- Molecular diagnosis for rhinovirus, adenovirus, picornavirus, RSV, influenza A and B, parainfluenza 1-3, human metapneumovirus, *M. pneumoniae*, *C. pneumoniae*, *L. pneumophila*
- Sequencing of viral PCR targets for confirmation and identification of mutations

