ANNEX 4 :

COLLECTE DE DONNEES PREDI-COVID

Utilisation de l'application smartphone

CoLive LIH (optionnel)

Français

V1.0

Suivi à distance depuis un smartphone ou tablette :

- 1 enregistrement vocal tous les jours de J0-J14 puis une fois par semaine dans les semaines 3 et 4, puis une fois par mois de M2 à M12

Table des matières

[figure not shown]
[Enregistrement de la voix sur smartphone](#)

Enregistrement de la voix sur smartphone

Pour l'identification de biomarqueurs vocaux associés à un syndrome respiratoire, la fatigue, à l'anxiété ou aux émotions en lien avec Covid19

Composé de 2 enregistrements

1. Enregistrement standardisé d'un texte pendant 30 secondes
2. Enregistrement d'un son "AAAAA" le plus longtemps possible par l'individu sans reprendre sa respiration.

Only for up to 300 household members of Predi-Covid participants

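### Recruitment can place several infected members of one household in the same analysis set, but section 11.4 names methods that in standard form assume independent participants and makes no provision for clustering

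*Protocol*

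**What the plan says.** All statements are in the protocol.

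- **Who can enter.** Section 5 opens the cohort to "virtually all adults ≥ 18 years and all children < 18 years with confirmed COVID-19 infection". Under section 6.4 every positive person is approached, so relatives who test positive can each be recruited directly.
- **The household route.** Predi-COVID-H enrols household members of sub-sample cases. Under section 7.3, "contacts with positive PCR will be proposed to be enrolled in the Predi-COVID cohort". Contacts who stay negative remain in the ancillary cohort.
- **Planned contacts.** The synopsis says "A minimum of 100 participants (adults and children) will be included in the sub-study on house-members", and Annex 4 carries the line "Only for up to 300 household members of Predi-Covid participants".
- **Analysis population.** Section 11.3 reads in full "All patients enrolled". There is no one-per-household rule.
- **Methods.** Section 11.4 says "A logistic model will be used to study whether the risks of hospitalisation, intensive care admission or intubation as well as death are associated"; the factor is left open, and the model is adjusted for age, gender and other confounders. For severity it says: "Factors triggering the severity of the disease will be evaluated with a Mantel-Haenszel chi square". No stratification variable is named. Neither household clustering, random effects, GEE nor robust variance appears anywhere.
- **Conversion.** Section 11.4 also says "The time to conversion from the PREDI-COVID-H cohort to the PRECOVID cohort will also be studied", without naming a model.
- **Candidate factors.** Household income and dwelling size are collected in Annex 2. Viral strain is a pathogen biomarker in section 2.2. Mutations and HLA genotypes are listed in section 4.2.

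**The concern.** Two infected members of one home share exposure, socio-economic position, probably the infecting strain and, if blood relatives, part of their genotype. If their outcomes are positively correlated after adjustment, they carry less information about a household-level factor than two unrelated people. An analysis that counts them as independent gives intervals that are too narrow for that factor and rejects too often.

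The factors exposed to this are among those the study wants to examine: strain or mutation, household income, dwelling and, in part, HLA. At stake is reporting such a trait as a severity factor on data that partly repeat the same household. The risk is greatest in the biosampled sub-sample, whose index cases are the ones whose household members are deliberately recruited.

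**Working it through.** **Inputs from the protocol.** Sub-sample of at least 200 adults and 100 children, total 300 (section 6), or 320 adults and 100 children, total 420 (section 5). At least 100 household contacts (synopsis), or up to 300 (Annex 4). Severe-disease prevalence 7% (section 11.2).

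**Assumptions, because the protocol is silent.** Two-sided alpha 5% (none is stated, and section 11.1 gives the hypotheses as not applicable); ICC of the outcome within households, 0.05 to 0.3; the number of contacts who convert; and the share *f* of participants in households with *m* enrolled members. The plan contains no figure of its own on clustering to reproduce.

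**Formulae for a factor fully shared within the household.**

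- Design effect: DE = 1 + *f* × (*m* − 1) × ICC
- Standard error assuming independence, relative to the true one: 1/√DE
- Actual type I error: 2 × (1 − Φ(1.96/√DE))

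**Diluted case.** Each converted contact pairs with one index case in the sub-sample, and everyone else is alone. Then *m* = 2 and *f* = 2 × converts/N.

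| Converts | N | *f* | DE, ICC 0.05 | Type I | DE, ICC 0.3 | Type I |
|---|---|---|---|---|---|---|
| 30 | 300 | 60/300 = 0.20 | 1.010 | 5.1% | 1.060 | 5.7% |
| 50 | 300 | 100/300 = 0.33 | 1.017 | 5.2% | 1.100 | 6.2% |
| 90 | 420 | 180/420 = 0.43 | 1.021 | 5.2% | 1.129 | 6.5% |

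**Everyone in a multi-member household (*f* = 1).**

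| *m* | ICC | DE | SE ratio | Type I | Effective N of 200 |
|---|---|---|---|---|---|
| 2 | 0.05 | 1.05 | 0.976 | 5.6% | 190 |
| 2 | 0.30 | 1.30 | 0.877 | 8.6% | 154 |
| 3 | 0.05 | 1.10 | 0.953 | 6.2% | 182 |
| 3 | 0.30 | 1.60 | 0.791 | 12.1% | 125 |

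**Simulation check.** The single-stratum Mantel-Haenszel chi-square was run on beta-binomial household outcomes at 7% risk and N = 200, with 20,000 runs per scenario. For a shared factor it rejected in 5.2% of runs with no multi-member households. With half the participants in pairs it rejected in 5.6% at ICC 0.1 and 6.7% at ICC 0.3. With 90% in trios it rejected in 6.6% and 11.4%. For a factor varying independently within households it stayed between 4.7% and 5.3% throughout.

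**Partly shared factors.** The excess scales with the factor's own within-household correlation. At an assumed 0.5, as might apply to HLA among relatives, the *m* = 2, ICC 0.3 case becomes DE = 1 + 0.5 × 0.3 = 1.15, and type I error falls from 8.6% to 6.8%.

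**The Mantel-Haenszel test.** Stratifying by household would not rescue it for these factors. A fully shared factor does not vary within a household stratum, so there would be nothing to test.

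**The case against.** The strongest objection is that section 11.4 names a model, not a variance estimator. A logistic model can carry clustered errors, and a protocol may leave that to an SAP, which is not at hand. For the logistic model this largely stands: the model itself need not change. It carries less weight for the Mantel-Haenszel chi-square, which is fixed by name and has no household adjustment in standard form, so an SAP would have to modify or replace it.

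A reader might infer that whole households enter one analysis set and that standard errors are therefore simply too small. The documents do not support that. Contacts enter a separate cohort, only consenting PCR-positive members move across, and the understatement needs positive residual correlation. A reader might also take 8.6% or 12.1% as the expected error. Those values require every participant to be in a pair or trio at ICC 0.3, and the protocol supports neither premise.

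Further points that stand:

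- Adjustment for age and gender may absorb some of the correlation.
- Adults and children are sized separately in section 11.2. If they were also analysed separately, parent-child pairs would not cluster.
- HLA is only partly shared among blood relatives, and not between spouses.
- Section 11.4 promises to discuss limits arising from participant selection.
- No model is named for time to conversion, so no error can be charged there.

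In the other direction, relatives recruited directly under section 6.4 add clusters that the diluted table omits, and the protocol does not quantify them.

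**Conclusion.** The point holds in conditional form. Recruitment creates household clusters, the analysis population keeps them, and section 11.4 names two methods that in standard form ignore them. For household-shared factors the understatement is small under the documented contact route alone: type I error about 5.1% to 6.5% under the assumptions shown. It becomes material only if many households contribute several cases and the ICC is sizeable. For factors that vary between members of a household there is essentially no problem. The size rests on an assumed alpha, ICC and conversion count; none of these can be read from the protocol. It merits correction because the remedy is cheap and alters results only where clustering exists.

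**What to change.** In section 11.4, keep the logistic model and state that its variance is clustered by household (sandwich errors, or GEE with household as the cluster). Base the Mantel-Haenszel comparison on the corresponding cluster-robust test. Alternatively, add a sensitivity analysis with one person per household.

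Carry a household identifier in the pooled dataset. Section 10 describes a single pseudonym per patient for linkage and mentions no household key. Build the identifier from the index-contact link and, where it can be derived, extend it to relatives recruited directly, whom that link misses. Do this before the adult correspondence table is deleted five years after study end (section 14), so that later users of the stored data can still account for clustering.

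For time to conversion, using the same household-robust variance is a suggestion only.

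The cost is a sentence or two of text and one derived variable. Recruitment, sampling and follow-up do not change. Intervals for household-shared factors widen by √DE: about 6% at DE 1.129 (√1.129 = 1.06), and about 26% in the all-trios case at ICC 0.3 (√1.6 = 1.26). Other factors are almost unchanged. The one-per-household option costs some sample size.
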